9.1.5 Analysis of Baseline Characteristics

The following baseline parameters will be described:

- Age
- Weight
- Hematology
- Serum chemistries
- ECOG performance status
- HSV status

Descriptive statistics for all baseline characteristics will be provided. No tests of significance will be conducted.

9.1.6 Patient Disposition and Agent Exposure

The number of patients treated with intraperitoneal talimogene laherparepvec will be summarized using descriptive statistics. Treatment delays will be summarized using counts and percentages.

Patients' disposition will be summarized in the following manner:

- The number and percentage of patients selected, included, completed, withdrawn and lost to follow-up will be summarized using descriptive statistics
- Major protocol deviations will be summarized.
- The reason for withdrawal (adverse events, lack of efficacy, major protocol deviation, non-medical reason, recovery or remission) will be summarized.

10.0 SAFETY

Refer to *Study Manual* for required reporting forms.

10.1 Adverse Events

An adverse event (AE) is defined as any untoward medical occurrence in a patient or clinical investigation subject administered a pharmaceutical product and which does not necessarily have to have a causal relationship with this treatment. An adverse event can therefore be any unfavorable and unintended sign (including an abnormal laboratory finding, for example), symptom, or disease temporally associated with the use of a medicinal product or protocol-specified procedure, whether or not considered related to the medicinal product or protocol-specified procedure. Any worsening (i.e., any clinically significant adverse change in frequency and/or intensity) of a preexisting condition that is temporally associated with the use of the supporting company product(s), is also an AE.

Changes resulting from normal growth and development that do not vary significantly in frequency or severity from expected levels are not to be considered AEs. Examples of this may include, but are not limited to, teething, typical crying in infants and children and onset of menses or menopause occurring at a physiologically appropriate time.

Supporting company product includes any pharmaceutical product, biological product, device, diagnostic agent or protocol-specified procedure, whether investigational (including placebo or active comparator medication) or marketed, manufactured by, licensed by, provided by or distributed by the supporting company for human use.

AEs may occur during the course of the use of supporting company product(s) in clinical trials or within the follow-up period specified by the protocol, or prescribed in clinical practice, from overdose (whether accidental or intentional), from abuse and from withdrawal.

Progression of the cancer under study is not considered an AE unless it is considered to be drug related by the Investigator.

AEs will be documented from the date of first dose of study drug through 30 days after the last dose of study drug. All Grade 2-5 AEs as well as special reporting circumstances, such as exposure via a parent during pregnancy or breast-feeding, overdose, medication error, misuse, abuse, off-label use or occupational exposure must be recorded on the CRF.

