5.1 Screening Period

During the Screening Period, subjects are consented and screened for the study. Informed consent must be obtained before initiation of any screening procedure that is performed solely for the purpose of determining eligibility for this study. Evaluations performed as part of routine care before informed consent can be considered as screening evaluations if done within the defined screening period, and if permitted by the local Institutional Review Board (IRB) / Independent Ethics Committee (IEC) policies. Study eligibility is based on meeting all of the inclusion criteria and none of the exclusion criteria (refer to [Section 4.0](#)) before the first dose of study drug on Cycle 1 Day 1.

The following study procedures must be done within 28 days prior to Cycle 1 Day 1:

- Demographics
- Medical and cancer history
- Concomitant medications
- Physical examination
- Abdominal measurement
- Height
- Vital signs and weight
- ECOG performance status
- Adverse event assessment (review of baseline symptoms)
- Tumor assessment (CT and/or MRI scans)
- Blood tumor marker, if clinically indicated (e.g., CEA or CA19-9)
- Whole blood (for pharmacogenomics) (may be collected pre-dose on Cycle 1 Day 1)
- Coagulation tests (must be done prior to catheter placement)
- Peritoneal catheter placement (must be placed after confirmation of eligibility)

The following study procedures must be done within 7 days prior to Cycle 1 Day 1:

- CBC with differential
- Chemistries including liver function tests (LFTs)
- Serum pregnancy test (only for women of childbearing potential)

Subject eligibility is determined using lab results obtained prior to peritoneal port placement and up to 7 days prior to Cycle 1 Day 1. The Screening Period ends upon placement of the peritoneal port or final determination that the subject is ineligible for the study. Patients with pre-existing peritoneal ports for standard of care treatment are eligible for participation. For these patients the Screening Period ends upon receipt of the first dose of study drug or final determination that the subject is ineligible for the study.

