5.2 Peritoneal Catheter Placement

After confirmation of patient eligibility, the peritoneal catheter must be placed prior to initiation of treatment. Catheter placement must occur on Day -4 (+/- 2 days) prior to C1D1.

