5.4 Follow-up Period

Subjects should return 30 (± 7) days after their last dose of study drug for an off-treatment visit to complete the following study procedures:

- Physical examination
- Abdominal measurement
- Vital signs and weight
- Concomitant medications
- ECOG performance status
- Adverse event assessment
- CBC with differential
- Chemistries including LFTs
- Serum pregnancy test (only for women of childbearing potential)
- Viral load (at disease progression and 30 day off treatment follow up)
- Peritoneal cytokines (at disease progression or off treatment, and 30 day off treatment follow up)
- Immune cells (at disease progression or off treatment, and 30 day off treatment follow up)
- Plasma (at disease progression or off treatment)

At the time of the follow up visit, the treating physician can determine whether or not to remove the IP catheter. If they anticipate using it for other IP therapies, it can be left in. If catheter is removed, treating physician may also determine whether it is clinically indicated to do PT/PTT. Additional follow-up may occur for subjects with adverse events (AEs) related to study drug that are ongoing at the time of this off-treatment visit unless AE is deemed unresolvable or subject has started a new anti-cancer treatment regimen.

For long-term follow up, subjects will be followed for progression every 12 weeks or as indicated until disease progression or start of new anti-cancer therapy. For subjects that complete or discontinue treatment without documented disease progression, subjects will have disease status (blood tumor marker(s) and restaging scans with RECIST 1.1 evaluation every 12 weeks) followed until disease progression or start of new anti-cancer treatment regimen.

All subjects will be followed for survival for up to 1 year after completing treatment. Survival status may be collected by personal interviews or review of medical records.

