6.2.2 Administration

All eligible subjects will have a Bard peritoneal catheter placed prior to the initiation of therapy. Talimogene laherparepvec will be administered via intraperitoneal (IP) administration. The planned dose of talimogene laherparepvec (measured as plaque forming units or PFU) will be delivered in a 500 mL volume of normal saline. After the infusion, patient should roll to the right side, wait 10 minutes, then roll to the left side and wait an additional 10 minutes, and repeat this procedure of rolling to the right side and the left side every 10-15 minutes to ensure exposure of the virus to the peritoneal surfaces where disease is located. Patients will have vital signs (blood pressure, pulse, temperature, and respiratory rate) taken every 15 minutes for the first hour after infusion, then remain under observation for an additional hour to ensure no significant toxicity is endured as a result of the administration. At the end of the second hour, vitals should be taken again prior to discharge. This procedure should be repeated each of the 5 potential times that talimogene laherparepvec is administered throughout the course of the study.

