10.2 Serious Adverse Events

A serious adverse event (SAE) is defined as any untoward medical occurrence that at any dose:

1. Results in death.
2. Is immediately life-threatening (ie, in the opinion of the Investigator, the AE places the subject at immediate risk of death; it does not include a reaction that, had it occurred in a more severe form, might have caused death).
3. Requires inpatient hospitalization or results in prolongation of an existing hospitalization.
4. Results in persistent or significant disability or incapacity. (Note: The term "disability" refers to events that result in a substantial disruption of a subject's ability to conduct normal life function.)
5. Is a congenital anomaly or birth defect.

6. Is an important medical event (Note: The term “important medical event” refers to an event that, based upon appropriate medical judgment, may not be immediately life-threatening or result in death or hospitalization, but may jeopardize the subject or require intervention to prevent one of the other serious outcomes listed under the definition of SAE. Examples of important medical events include intensive treatment in an emergency room or at home for allergic bronchospasm; blood dyscrasias, or convulsions that do not result in hospitalization; or development of product dependency or product abuse.)

SAEs and/or follow up to SAEs including death due to any cause other than progression of the cancer under study, that occurs from the date of the first dose of study drug through 30 days following the last dose of study drug, whether or not related to study drug(s), must be recorded on the CRF and must be reported within 2 working days to Amgen (please see section below for instructions on how to report to Amgen). External sites should report SAEs to the Duke study team within 24 hours. Reporting instructions for external sites can be found in the REDCap study eManual.

All SAEs must be followed until resolution, return to baseline condition, or stabilization. Any SAEs that are ongoing at the time the clinical database is closed will be reported to supporting companies as unresolved.

The initial report for each SAE or death should include at minimum the following information:

- protocol number and title
- patient initials, study identification number, sex, age
- date the event occurred
- description of the event
- seriousness criteria
- event causality or causal relationship
- study drug name(s)

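### AE and SAE collection opens at first dose, so complications of on-study catheter placement in the preceding 2 to 6 days need not be captured

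*Combined protocol and SAP*

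**What the plan says.** **Collection window.** Section 10.1: "AEs will be documented from the date of first dose of study drug through 30 days after the last dose of study drug". Section 10.2 requires CRF recording, and reporting to the supporting company within 2 working days, for an SAE "that occurs from the date of the first dose of study drug through 30 days following the last dose of study drug", whether or not it is drug related.

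**What counts as an AE.** The definition in 10.1 covers events "temporally associated with the use of a medicinal product or protocol-specified procedure".

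**The catheter.** Section 6.2.2: "All eligible subjects will have a Bard peritoneal catheter placed prior to the initiation of therapy". Section 5.2: "Catheter placement must occur on Day -4 (+/- 2 days) prior to C1D1". Appendix C gives the same window as Day -6 to -2. There is one exception, in 5.1: "Patients with pre-existing peritoneal ports for standard of care treatment are eligible for participation".

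**Before first dose.** The AE item in the 5.1 screening list is a review of baseline symptoms. For patients who receive a port on study, screening closes when the port is placed.

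**Statements that point the other way.** Section 5.6 and Appendix C footnote 4 call for AE documentation over the whole study and give no start date.

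**Analysis set.** Section 9.1 limits the safety population to patients who received study drug, and 9.1.2 runs the primary safety analysis on that population.

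**End of the window.** Section 5.4: "Subjects should return 30 (± 7) days after their last dose of study drug". Section 7.0 requires continuous AE monitoring until 30 days after the last dose and has subjects told to report every AE.

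**The concern.** The definition admits procedure-related events, but the collection clock shuts out the period right after the one invasive procedure that the protocol imposes before treatment. The protocol treats placement as carrying risk: 4.2 excludes bleeding disorders that would preclude a port and recent infection or fever, and 5.1 requires coagulation tests beforehand.

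The primary objective is the toxicity profile of intraperitoneal treatment, and 1.3 speaks of the safety of intraperitoneal delivery. The synopsis plans 12 to 24 evaluable patients, so a single serious placement complication would be a material finding. If it stopped the patient from being dosed, neither the AE rules nor the safety population would bring it into the safety tables.

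Attribution is also affected. For on-study ports, 5.1 takes eligibility laboratory tests before placement, and 5.3 uses the Day -7 to -3 results as the C1D1 values. A laboratory change caused by placement may first show at Day 8, after dosing, with no AE record of the days between.

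**Working it through.** No sample-size or error-rate formula applies. The check is window arithmetic plus a comparison of sections.

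**1. Reproduce the placement window.** From 5.2: -4 - 2 = Day -6, and -4 + 2 = Day -2. This agrees with Appendix C.

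**2. Length of the gap.** Placement precedes C1D1 by 2 to 6 days (3 to 7 if a Day 0 is counted). Collection under 10.1 and 10.2 starts on C1D1, so this whole interval lies outside it.

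**3. Does another section fill the gap?**
- 5.1 screening: baseline symptoms only, and screening is over at placement. It does not.
- 5.3, C1D1 visit: a physical examination and AE assessment are done, so an ongoing complication should be noticed. Section 10.1 still does not require an event with pre-dose onset to be recorded as an AE, and a patient who never reaches C1D1 has no such visit.
- 5.6 and Appendix C footnote 4: broad enough to cover the gap if read literally, but undated and in conflict with 10.1. Neither alters the SAE start in 10.2.
- 6.3.1: concomitant medications are recorded from consent, so drug treatment of a complication is documented, but not the event itself.
- 3.1 and 9.1.6: withdrawal before dosing is foreseen, and reasons for withdrawal, including adverse events, are summarised. An undosed patient appears as a disposition count, not as a graded event.
- 10.2: local IRB reporting, and IRB reporting of a study-related death within 24 hours, are stated without a first-dose start.

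**4. Share of the catheter period affected.** With all doses on schedule, C4D1 is study day 1 + 35 + 14 + 14 = 64, and collection runs to day 64 + 30 = 94. The pre-dose gap is then 2/(94 + 2) = 2.1% to 6/(94 + 6) = 6.0% of the period from placement to the end of collection.

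**5. Illustration of scale.** The documents give no placement complication rate, so the rates below are assumptions. With p the chance of a pre-dose event per patient, the chance of at least one in n newly catheterised patients is 1 - (1 - p)^n.

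| Assumed p | n = 12 | n = 24 |
|---|---|---|
| 1% | 11% | 21% |
| 2% | 21% | 38% |
| 5% | 46% | 71% |
| 10% | 72% | 92% |

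**6. Off-treatment visit.** 30 - 7 = Day 23 and 30 + 7 = Day 37 after the last dose. If the visit is on Day 23, Days 24 to 30 have no scheduled assessment: 7 of 30 days, or 23%. Those days remain inside the collection window under 7.0, 10.1 and 10.2.

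**The case against.** The strongest reply is that 5.6 already requires AE documentation over the whole study, so the matter is only one of consistency. That stands in part, since a site following 5.6 would record the event. But 5.6 refers to 10.1 for the AE definition, 10.1 is the section that gives a date, and 10.2 repeats that date for SAEs. Two readings of a collection rule behind the primary endpoint need the same edit either way.

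Several stronger readings are tempting, and the documents do not support them:

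- *Catheter complications in general are lost.* Infection, malfunction or pain with onset after first dose is inside the window, and patients with pre-existing ports have no placement gap.
- *Placement events escape all safety reporting.* The gap is in CRF recording and reporting to the supporting company. IRB reporting may still apply.
- *An undosed patient disappears.* The withdrawal and its reason are still counted in disposition.
- *The MTD is affected.* Section 3.2.1 counts only drug-related events as DLTs, and a pre-dose event cannot be one.
- *The trial will understate the risk of the route.* Without a complication rate in the documents, the size of any understatement is unknown.
- *Late events escape the endpoint because the visit can fall on Day 23.* Collection is set by date, not by visit, and 7.0 adds continuous monitoring and subject reporting. Only a guaranteed contact at the end of the window is missing. That has some weight for silent laboratory abnormalities, because this visit has the last scheduled blood tests.

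**Conclusion.** The point holds for the interval between on-study catheter placement and first dose. For each patient catheterised on study, 2 to 6 days after an invasive procedure required by the protocol fall outside the AE and SAE rules of section 10. This contradicts both the protocol's own AE definition and the whole-study wording in 5.6 and Appendix C. A complication that prevents dosing is also outside the safety population.

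This rests on taking the dated rules in 10.1 and 10.2 as governing. If 5.6 governs instead, the AE gap closes on that reading, but the contradiction and the SAE start date remain. The number of events at stake cannot be estimated from the documents; the table above is illustrative only.

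The Day 23 visit is a minor scheduling weakness, not a loss of data by rule. Both matters should be corrected. Neither undermines the dose-escalation decisions.

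**What to change.** - **10.1 and 10.2:** start AE and SAE collection at on-study catheter placement, and at first dose for patients with a pre-existing port.
- **5.6 and Appendix C:** state the same start, and mark an AE assessment at the catheter-placement step.
- **9.1 and 9.1.2:** add a separate listing of catheter-placement events covering every patient catheterised on study, including those never dosed. The safety population can stay as dosed patients for the drug-toxicity tables. Editing section 10 alone would not bring undosed patients into any safety output.
- **5.4 and Appendix C (minor):** change the off-treatment visit to 30 (+7) days, so that an assessment always falls at or after the end of the 30-day window.

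The cost is wording, one extra listing, a few more AE entries and slightly more reported events. The narrower visit window leaves sites less room for scheduling.

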2.0 OBJECTIVES

2.1 Primary Objective

The primary objective of this trial is:

1. To evaluate the toxicity profile of intraperitoneal talimogene laherparepvec in patients with peritoneal surface dissemination from gastrointestinal, fallopian tube, ovarian, or primary peritoneal tumors.

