3.2.1 Dose Limiting Toxicity

Toxicity should be evaluated and defined according to CTCAE version 5.0, and should only include events assessed as related to talimogene laherparepvec during treatment and up to 30 days after the last talimogene laherparepvec injection.

The following herpetic events should be considered as DLTs:

- Serious herpetic events such as herpetic encephalitis, encephalomyelitis or disseminated hepatic infection.
- Any herpetic events confirmed due to talimogene laherparepvec that require treatment with acyclovir or similar anti-viral agent. Talimogene laherparepvec treatment should be suspended if treatment is required with systemic acyclovir or other anti-virals. If ongoing anti-viral treatment is required, talimogene laherparepvec treatment should be permanently discontinued.

The following are also considered DLTs:

- Grade 3 or greater immune-mediated adverse events.
- Any grade plasmacytoma at or near the injection site or evidence of impaired wound healing at the injection site.
- Grade 3 or greater allergic reactions considered at least possibly related to talimogene laherparepvec.
- Grade 4 non-hematologic toxicity.
- Grade 3 non-hematologic toxicity lasting > 3 days despite optimal supportive care;
 - Grade 3 fatigue will not be classified as DLT, irrespective of duration.
- Any Grade 3 or higher non-hematologic laboratory value if:
 - Medical intervention is required, or
 - The abnormality leads to hospitalization, or
 - The abnormality persists for > 1 week unless deemed not clinically important per both treating physician and study PI or co-PI.
- Grade 3 or 4 febrile neutropenia.
- Grade 4 thrombocytopenia associated with bleeding event required intervention.
- Any other intolerable toxicity leading to permanent discontinuation of talimogene laherparepvec.
- Grade 5 toxicity (i.e., death).

If an unexpected DLT occurs, talimogene laherparepvec administration should be delayed until the DLT has resolved to at least CTCAE (v. 5.0) Grade 1. If talimogene laherparepvec dosing is delayed by more than 6 weeks from the date of the planned dose due to the occurrence of an adverse event that is

considered related to talimogene laherparepvec, the subject must be permanently taken off talimogene laherparepvec treatment.

Management and dose modifications associated with all adverse events are outlined in Section 7.0.

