9.1.2 Primary Endpoint

The primary objective of the study is to define the safety and toxicity profile of talimogene laherparepvec in patients with peritoneal surface dissemination from gastrointestinal, fallopian tube, ovarian, or primary peritoneal tumors. The MTD across three dose levels will be determined as described in Table 3.1. The safety analyses will be performed on the safety population, as defined above. Incidence of adverse events occurring in 10% or more of patients will be summarized by Grade, overall and by dose level.

Adverse events will be described using the NCI CTCAE 5.0 criteria. Frequency and severity of adverse events according to the NCI CTCAE v 5.0 body system and severity criteria will be described. In addition, frequency of Grade 3 or 4 adverse events will be described separately. Causality will also be noted.

Laboratory assessments will also be described according to the NCI CTCAE criteria, with separate descriptions for Grade 3 or 4 laboratory abnormalities. Clinically significant laboratory abnormalities will be described as well. Serious adverse events will be summarized, including a causality assessment.

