The Sponsor/Investigator is responsible for compliance with expedited reporting requirements for serious, unexpected and related adverse events (SUSARs), for generation of SAE reports including narratives, and for periodic reporting to Amgen of SAEs as outlined in the tables below. Documents sent to Amgen should be accompanied by the Cover Page provided in Appendix E. Documents may be faxed to the number provided on the cover page or scanned and sent via email to [contact].

In addition to the requirements outlined in the tables, Sponsor/Investigators are required to report direct exposures to talimogene laherparepvec (e.g., needle stick, splash back) of herpetic illness and all suspected herpetic events.

Table 10.2.1 Reporting Requirements for Interventional Studies

Safety Data	Timeframe for Submission to Amgen
Suspected Unexpected Serious Adverse Reaction (SUSARs)	Individual reports sent to Amgen at time of expedited reporting to IRB and/or FDA.
Serious Adverse Events (SAEs) (related)	Individual reports sent to Amgen at time of expedited reporting to IRB and/or FDA
Pregnancy/Lactation	Individual reports sent within 10 days of Sponsor/Investigator awareness.

Table 10.2.2 Aggregate Reports

Safety Data	Timeframe for Submission to Amgen
Adverse events (all serious and non-serious adverse events, regardless of relatedness)	Line listing and summary tabulation of all adverse events sent annually AND at end of study
US IND Annual Safety Report	Annually
Other Aggregate Analyses (any report containing safety data generated during the course of the study)	At time of ISS sponsor submission to any body governing research conduct (e.g., RA, IRB, etc.)
Final (End of Study) Report, including: 
 • Unblinding data for blinded studies 	At time of ISS sponsor submission to any body governing research conduct (e.g., RA, IRB, etc.) but not later than 1 calendar year after study completion

• Reports of unauthorized use of a marketed product	
---	--

Expedited Reporting Procedure for Duke Cancer Institute (Coordinating Center):

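### Non-serious Grade 1 adverse events, including any that meet a grade-free DLT criterion, have no mandatory CRF record, so the by-grade toxicity summary and the all-AE listing cannot be produced completely from the database

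*Combined protocol and SAP*

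**What the plan says.** **Objective.** Section 2.1 sets the primary objective: "To evaluate the toxicity profile of intraperitoneal talimogene laherparepvec in patients with peritoneal surface dissemination".

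**CRF rule.** Section 10.1 first defines the period: "AEs will be documented from the date of first dose of study drug through 30 days after the last dose of study drug". That sentence has no grade floor. The next one, which says what must be entered on the CRF, does: "All Grade 2-5 AEs as well as special reporting circumstances".

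**Primary analysis.** Section 9.1.2 plans: "Incidence of adverse events occurring in 10% or more of patients will be summarized by Grade, overall and by dose level". It adds: "Frequency and severity of adverse events according to the NCI CTCAE v 5.0 body system and severity criteria will be described". It then says: "In addition, frequency of Grade 3 or 4 adverse events will be described separately". The separate Grade 3 or 4 description is an addition, so the main summary is meant to be wider. No lower grade limit is given.

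**DLTs.** Section 3.2.1 includes: "Any grade plasmacytoma at or near the injection site or evidence of impaired wound healing at the injection site". Plasmacytoma counts at any grade, and impaired wound healing has no grade attached.

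**Aggregate reporting.** The line listing and tabulation in Table 10.2.2 (Section 10.2), due yearly and at study end, cover: "Adverse events (all serious and non-serious adverse events, regardless of relatedness".

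**The concern.** The mandatory content of the database starts one grade above what the primary summary and the aggregate listing appear to need. A site that follows Section 10.1 to the letter may leave a non-serious Grade 1 event off the CRF. Three things then suffer.

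- The by-grade table has no dependable Grade 1 column. If some sites enter Grade 1 events and others do not, the column is worse than absent, because it mixes sites with different capture.
- Incidence counts patients. A patient whose only experience of a term was Grade 1 is missing from the numerator, so incidence is understated and a term can fall below the 10% threshold.
- A mild wound-healing problem or a non-serious Grade 1 plasmacytoma is a DLT by definition but has no required CRF entry, so the DLT count cannot be rebuilt from the database alone.

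Any dose trend in this small trial may lie mainly in low-grade events, so the gap bears on the primary endpoint.

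**Working it through.** This is a question of data capture. The plan states no figure to reproduce, and no sample size or error rate depends on it.

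**1. What reaches the CRF at which grade**

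| Event type | Required on CRF | Source |
|---|---|---|
| AE of Grade 2 to 5 | Yes | Section 10.1 |
| Special reporting circumstances | Yes, no grade floor | Section 10.1 |
| Serious AE | Yes, no grade floor | Section 10.2 |
| Laboratory abnormality that changes management | Yes, no grade floor | Section 5.5 |
| Concomitant medication, including an antiviral | Yes | Section 6.3.1 |
| Non-serious clinical Grade 1 AE | Not required anywhere | – |
| DLT as such | Not required anywhere | – |

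The last two rows are the gap. The summary in Section 9.1.2 and the listing in Table 10.2.2 both extend into the first of them. The two grade-free criteria quoted from Section 3.2.1 can fall into both.

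**2. How much of the expected profile is low grade**

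The inputs are the protocol's adverse reaction table (Table 1.2.1.3, melanoma, N = 292) for its six most frequent terms. None has a Grade 5 case. I take each patient as counted once per term.

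| Term | All | Grade 3-4 | Below Grade 3 |
|---|---|---|---|
| Fatigue | 147 | 5 | 142 |
| Chills | 142 | 0 | 142 |
| Pyrexia | 125 | 0 | 125 |
| Injection site reactions | 115 | 3 | 112 |
| Nausea | 104 | 1 | 103 |
| Influenza-like illness | 89 | 2 | 87 |
| Total | 722 | 11 | 711 |

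Share below Grade 3 = (722 − 11) / 722 = 711 / 722 = 98.5%.

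The table does not separate Grade 1 from Grade 2. The Grade 1 share is therefore bounded only by 0% and 98.5%. Serious events reach the CRF at any grade, which trims the ceiling slightly. The 5 serious pyrexia and 1 serious chills cases must be below Grade 3, because neither term has a higher-grade case. That gives (711 − 6) / 722 = 705 / 722 = 97.6%.

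**3. Interaction with the 10% threshold**

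The smallest patient count that meets 10% is 2 of 12 (10% = 1.2), 3 of 24 (10% = 2.4) and 3 of 30 (10% = 3.0). As an illustration with assumed counts, take a term seen in 4 of 24 patients, two of them Grade 1 only. True incidence is 4 / 24 = 16.7%. From a Grade 2 to 5 database it is 2 / 24 = 8.3%, and the term leaves the table.

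**4. What would have to be assumed for an effect on escalation**

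Under the 3+3 rule in Section 3.2 (escalate on 0 of 3 or 1 of 6), with DLT rate p and q = 1 − p:

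P(escalate) = q³ + 3p·q⁵.

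If a share s of DLTs went uncounted, p is replaced by p(1 − s). Both p and s are assumptions.

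| p | s = 0 | s = 10% | s = 25% | s = 50% |
|---|---|---|---|---|
| 0.20 | 0.709 | 0.752 | 0.814 | 0.906 |
| 0.30 | 0.494 | 0.557 | 0.654 | 0.814 |

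These are upper-end scenarios. They need s to be the share of DLTs that the escalation reviewers never see, not the share absent from the CRF. The documents give no value for s, and few DLT categories can be Grade 1 at all.

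**The case against.** The best defence is that Section 10.1 sets a minimum and does not bar Grade 1 entries. Severity notes for all adverse events are kept in source (Section 11.5), the CRF is verified against source (Section 11.6), and the Lead PI continuously tabulates adverse events (Section 11.7). The Study Manual and CRF completion guidelines are not among the documents and may ask for more. Table 10.2.2 does not say that its listing must come from the CRF. All of this stands, and it rules out several stronger readings.

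- **That Grade 1 toxicity is lost.** A reader might infer this, but the events stay in source. What is missing is a required entry in the analysis database.
- **That one Grade 1 DLT missing from the CRF changes the escalation decision.** Sections 3.2 and 10.5 have the PI, co-PI and study chair review the safety data, with no restriction to CRF entries, after weekly visits in Cycle 1. Absence from the CRF is not absence from that review.
- **That treated herpetic DLTs go unrecorded.** Suspected herpetic events are reported to the supporting company within 24 hours with a lesion swab (Section 10.3.1), and the antiviral is entered as concomitant medication (Section 6.3.1). The documents also do not show that such an event could be Grade 1.
- **That Table 10.2.2 demands all grades in so many words.** Its qualifier concerns relatedness, not grade. Coverage of every grade follows only from the word all.

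Plasmacytoma is also a weaker example than wound healing. The single case in the protocol's table was Grade 3-4 and serious, so it would have been captured, and a milder one might be judged medically important and reported as serious.

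The defence does not close the gap. Source notes are not the analysis database, and the central monitoring described in Section 11.7 looks at one to three subjects a year after the first visit. No section requires a DLT to be identified on the CRF.

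**Conclusion.** The point holds as an inconsistency between the data capture rule and the analyses that depend on it. As written, the primary by-grade summary and the all-AE listing cannot be produced completely from the database for non-serious clinical Grade 1 events, and a non-serious Grade 1 plasmacytoma or wound-healing DLT has no mandatory CRF record.

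The size cannot be fixed from the documents. The Grade 1 share of the six most frequent terms lies between 0% and 98.5%, and the figures come from intralesional use in melanoma, so they may not carry over to intraperitoneal use. An effect on dose escalation is possible but not shown. The conclusion assumes that sites apply Section 10.1 as worded and that the unseen Study Manual and CRF guidelines do not widen it. If they do, the protocol text still needs to agree with them.

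**What to change.** Preferred: change Section 10.1 so that adverse events of all grades go on the CRF from first dose to 30 days after the last dose, and add a DLT flag to the adverse event form.

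Minimum: require on the CRF every event that meets a DLT criterion and every related adverse event, at any grade. Then state in Section 9.1.2 and Table 10.2.2 that unrelated Grade 1 events are excluded, so that the incidence figures are read correctly.

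Either way, reconcile Sections 3.2.1, 9.1.2 and 10.1 and Table 10.2.2 so that the capture rule, the DLT list, the analysis and the listing cover the same events.

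The cost is more data entry in at most 24 patients (synopsis total) to 30 (Section 9.1 maximum). No design figure changes.
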